## **5. Trial methods**

### **5.1 Description of randomisation and code breaking**

The randomisation scheme will be generated by statisticians at CTEU Bristol, and supplied to the manufacturing pharmacy so that study drug and placebo can be labelled with appropriate randomisation label. The randomisation system will be part of the study database so that patient eligibility has to be confirmed before their randomisation number is revealed. The randomisation system will not reveal the actual allocation, therefore any team member who is authorised to use the study database may randomise.

Participants will be randomised in a ratio of 1:1 to study drug with usual care and placebo with usual care, and the randomisation scheme will take into account prognostic and other important factors. Randomisation will take place within in one month of the screening visit. Where this does not happen all screening tests (with exception of bloods samples taken for the biobank) must be repeated to ensure inclusion criteria are still met.

Unmasking will either be performed by CTEU Bristol or the local pharmacy at the request of the treating investigator.

### **5.2 Masking**

This is a double masked trial, as the intervention and placebo will appear identical. The treating investigator will be able to request unmasking of treatment in case of medical emergency. The chief investigator/co-lead will have the final decision and unilateral right to unmask allocation.

### **5.3 Research procedures**

We will collect 30mls of blood from patients to create a biobank of DNA, serum and plasma. Patients will have the opportunity to decline participating in this part of the study if they so wish. However our previous experience in the IVAN and other clinical trials is that most participants are happy to contribute to a biobank for future mechanistic studies.

Demographic data will be collected on participants but this will include demographic history, smoking history, medical history of significance, history of any steroid use and duration used and approximate duration since last usage.

Patients will undergo all study procedures on both eyes at each visit as dictated by the study protocol (see table 1 below). FFA, ICGA, AF and OCT imaging should be done using standard techniques, and it is mandatory that the AF and OCT must be performed using Heidelberg equipment. To obtain standardised autofluorescence measurements the eye should be bleached with laser light for 15 seconds before taking the AF image. The FFA and ICGA will be performed on the study eye first. Where OCT angiography equipment is available, OCT angiography should be carried out at baseline, or an interim follow-up visit if equipment becomes available a later date, and at the 12 month follow up.

### **5.4 Duration of treatment period**

See section 4.5

## **5.5 Definition of end of trial**

The end of the trial for a participant is at the completion of follow-up at 12 months (or earlier if a participant withdraws). The end of the trial as a whole is when all follow-up is completed, data collected and cleaned and the database is locked. DNA, serum and plasma will be banked after the end of the study under appropriate arrangements.

Ongoing treatment if the study is successful: All participants will be made aware of the results of the study. If the study successfully establishes efficacy, the patients will be informed of its efficacy. They will be able to continue the treatment if their primary physicians and ophthalmologists are happy to continue monitoring. Otherwise, they will be treated in accordance with normal standard of care if the disease recurs.

## **5.6 Data collection**

Data collection will include the following elements:

- (a) A log of patients presenting with CSCR and those who are approached for the trial (including the date when they are given the Patient Information Leaflet (PIL)).
- (b) Patients approached and assessed against the eligibility criteria and, if ineligible, reasons for ineligibility.
- (c) Consent and baseline information collected prior to randomisation. See Table 1 for data collected as baseline.
- (d) Treatment compliance – capsule count by pharmacy
- (e) Data to answer primary and secondary outcomes (see below)

**Table 1 Data collection**

	Time-point and visit number						
	Screening/ baseline	week 1	week 4	3 months	6 months	9 months	12 months
Data to be collected	0	1	2	3	4	5	6
Medical history	x						
Ophthalmic history	x						
Concomitant medications*6	x	x	x	x	x	x	x
Pregnancy test (women only)	x						
FFA	x						x
ICGA	x						x
AF	x						x
FP	x						x
BCVA (to include binocular BCVA)	x		x	x	x	x	x
Low luminance BCVA	x		x	x	x	x	x
OCT with EDI*1	x		x	x	x	x	x
OCT angiography*5 *7	x	x	x	x	x	x	x
DNA, serum and plasma*2	x						
Hba1c*3	x						x
Thyroid function tests*3	x						x
Full blood count (FBC) *3	x						x
Liver function tests*3	x						x
Urea and electrolytes profile*3 *4	x	x	x	x	x	x	x
Blood pressure measurement	x	x	x	x	x	x	x
Heart rate measurement	x	x	x	x	x	x	x
Slit lamp examination	x		x	x	x	x	x
Adverse event form	x	x	x	x	x	x	x
VFQ-25	x						x

\*1 Images at baseline & 12 months to be graded by Independent Reading Centre at NetWORC UK. Images from other at time points to be graded by specialists within the study team.

\*2 Samples sent to Southampton hospital laboratory.

\*3 Tests conducted at local hospitals.

\*4 To include creatinine

\*5 Where equipment available

\*6 At each visit we will check whether patients are taking any drugs that have been shown to treat CSCR (e.g. rifampicin, finasteride, melatonin).

To minimise bias, outcome measures are defined as far as possible on the basis of objective criteria. All personnel carrying out outcome assessment will be masked; this will minimise detection bias. Biochemical markers will be measured by an independent laboratory technician, without knowledge of treatment allocation.

\*7 A maximum of two OCT angiography image sets will be collected per participant. OCT angiography will be collected at baseline, or at an interim time-point if imaging equipment is not available at baseline, and at 12 months.

#### Visit windows

Week 1 (+/-1 day)

Week 4 (+/- 5 days)

All other follow up visits (+/- 10 days)

### **5.7 Source data**

The source data will be made up of the patient's medical records, questionnaires, CRFs, visual acuity score sheets, images from FFA, ICGA, AF and OCT, FP, image grading data files and outputs from blood tests including but not limited to hospital pathology reporting systems.

### **5.8 Planned recruitment rate**

Recruitment is expected to take 12 months. Participating sites have confirmed that they can recruit 5 patients in one year.

### **5.9 Participant recruitment**

Patients presenting with CSCR will be invited to participate. Patients will be identified and approached according to local procedures. At some hospitals patients may be identified through hospital databases and initially contacted by the study team by phone/email. All potential participants will be sent or given an invitation letter and PIL (approved by a Research Ethics Committee (REC)) describing the study. The patient will have time to read the PIL and to discuss their participation with others outside the research team (e.g. relatives or friends) if they wish. Most patients will have at least 24 hours to consider whether to participate.

Potential participants will be seen by a member of the local research team (study clinician/ research nurse/trial co-ordinator) in clinic who will answer any questions, confirm the patient's eligibility and take written informed consent if the patient decides to participate. The PI or a delegated doctor must confirm the eligibility prior to randomisation. Details of all patients approached for the trial and reason(s) for non-participation (e.g. reason for being ineligible or patient refusal) will be documented.

Patients will be identified from searching hospital administration systems for existing patients as well as from patients attending clinics.

### **5.10 Discontinuation/withdrawal of participants**

It is important to distinguish cessation of treatment (drug or placebo) from withdrawal from the trial. Participants have the right to request cessation of treatment (and may simply not take trial tablets) or to withdraw from the study at any time, without giving a reason. An excessive rate of withdrawals can render the study uninterpretable. Therefore, it is desirable to avoid participants stopping treatment or asking to withdraw from the trial. Should a patient decide to withdraw from the study, all efforts will be made to report the reason for withdrawal as thoroughly as possible. Moreover, participants who wish to withdraw from the study because they want to stop treatment will be asked to confirm whether they are still willing to attend study visits for outcome assessments, in particular the end-of study visit at month 12.

If a participant wishes to withdraw, we will continue to analyse any data already collected, unless the participant expresses a wish for their samples and any associated data to not be used.

If individual participants meet any of the following criteria they will be told to stop taking the trial treatment (drug or placebo): any adverse events that in the opinion of the investigator may jeopardise the safety of the trial participant; pregnancy. If there is disease progression or worsening (15 or more letter decrease in BCVA) the treating ophthalmologist may use other therapies and/or stop study drug (see Treatment decisions in section 4.5).

### **5.11 Frequency and duration of follow up**

The participants will be followed up at: 1 and 4 weeks, and 3, 6, 9, and 12 months.

### **5.12 Likely rate of loss to follow-up**

Clinical trials on retinal conditions that require regular follow-up visits have shown that approximately 5% withdraw consent and 5% are lost to follow-up. Our previous clinical trial experience on retinal conditions demonstrates that the patients' attendances in relation to the trial schedule are good because of their fear of visual loss. The usual cause of non-adherence with study visits is due to co-morbidities and we have estimated this to be <15%. Statistical analyses will include data for all participants up to the time of completion of follow-up or withdrawal from the trial and will accommodate missing data for some visits (assumed to be missing at random) with only minor loss of power.

### **5.13 Expenses**

Patients will be reimbursed for travel expenses for all study visits.

## **6. Statistical analyses**

### **6.1 Plan of analysis**

The statistical analysis plan will be written prior to any comparative analyses.

Outcomes measured at multiple time points (e.g. BCVA) will be compared between the two treatment groups using mixed models for repeated measures, adjusting for baseline. Mixed models allow all patients with data to be included in the analysis, i.e. partial missing data (assumed missing at random) is permitted. Appropriate transformations of continuous outcomes may be applied if necessary. Interactions between treatment and time will be examined and, if significant at the 5% level, a treatment by time interaction will be included in the model and the treatment effect at 12 months will be reported with 95% confidence intervals.

Non-adherence to random allocations will be documented. With the exception of adverse events the trial will be analysed on an intention-to-treat basis, i.e. outcomes will be analysed according to the treatment allocation, irrespective of future management and events, and every effort will be made to include all randomised participants. However we do not expect any crossovers due to the placebo-controlled design.

Non-adherence to drug/placebo will also be monitored and this information will be included in reports prepared for the Trial Steering Committee. Depending on the level of adherence

observed, the statistical analysis plan for the trial may include additional analyses to investigate the interaction between adherence to medication and treatment.

Additional analyses of the overall trial cohort will investigate:

1. The association between final visual acuity and age of patient;
2. The association between presence of granular / confluent hypoautofluorescence in the macula at randomisation and final visual acuity.

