## 4.2 Trial design

This is a multicentre, individually randomised, double-masked, placebo-controlled trial that will test the superiority of eplerenone therapy with usual care to placebo with usual care at 12 months. The trial design has been formulated in consultation with the UKCRC-registered Clinical Trials and Evaluation Unit (CTEU) Bristol, a trial statistician, a methodologist involved in the Research Design Service, clinical research networks, service users and a group of ophthalmologists specialising in medical retina. The basic study design and the associated clinical measurements are well established. The superiority study design has also been successfully used in numerous previous clinical trials in medical retinal conditions. 104 adult patients with chronic CSCR will be randomised 1:1 to receive eplerenone with usual care or placebo with usual care for a period of 12 months.

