## 4.6 Primary and secondary outcomes

### 4.6.1 Primary outcome

The primary outcome is the BCVA at the 12 month visit, adjusted for baseline BCVA, measured using validated ETDRS vision charts with measurements made in accordance with a standardised protocol for trials in medical retina. Refracted visual acuity will be done at baseline, 4 weeks, 3, 6 9 and 12 months.

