## 4.7 Sample size calculation

A sample size of 45 patients in each of the 2 groups would be sufficient to detect a difference of 5 letters in BCVA between the eplerenone and placebo groups with 90% power and 5% significance (2-tailed), assuming that the standard deviation is 9 letters [14], the correlation between baseline and any follow up assessment is 0.5 [15], and that, on average, there will be a minimum of 2 follow up assessments per patient [16] with a correlation between BCVA on follow-up visits of 0.8. The total sample size has been increased to 104 to allow for up to 15% dropout over the 12 month period, which should be a conservative estimate in this patient

group. This sample size justification does not take into account the extra power that will be obtained from including data for two eyes, coded as CSCR or not.

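### A 5% test of treatment-by-time decides whether the primary result is the 12-month BCVA difference or a difference pooled from week 4 to month 12

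*Protocol*

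**What the plan says.** Protocol section 4.6.1 sets the outcome: "The primary outcome is the BCVA at the 12 month visit, adjusted for baseline BCVA". Section 4.2 sets the same time point for the hypothesis: the trial "will test the superiority of eplerenone therapy with usual care to placebo with usual care at 12 months". BCVA is recorded at five visits after baseline: "Refracted visual acuity will be done at baseline, 4 weeks, 3, 6 9 and 12 months".

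Section 6.1 gives the analysis. Outcomes measured repeatedly, with BCVA as the example, "will be compared between the two treatment groups using mixed models for repeated measures, adjusting for baseline". It then adds a condition: "Interactions between treatment and time will be examined and, if significant at the 5% level, a treatment by time interaction will be included". In that case the 12-month effect is to be given with its 95% confidence interval. The section does not say what is reported when the interaction is not significant.

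Section 4.7 begins "A sample size of 45 patients in each of the 2 groups" and bases that figure on a 5-letter difference, 90% power, two-sided 5%, SD 9, baseline correlation 0.5, and at least two follow-up assessments correlated at 0.8.

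**The concern.** A repeated-measures model without a treatment-by-time term has one treatment coefficient, shared by all visits. It can be called a 12-month effect only by assuming the effect is the same at week 4 as at month 12. A non-significant interaction in a trial of this size is weak evidence for that assumption.

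The data therefore choose which quantity answers the primary question, and the reported interval and p-value take no account of the choice. If benefit builds slowly, the 12-month effect is understated. If benefit is early and fades, the trial may claim a 12-month effect that is not there.

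The protocol gives reasons to expect some change over time. In section 2.3 the pilot's mean logMAR went from 0.52 to 0.34 at 1 month and 0.27 at 3 months. In one case series in section 2.4 it went from 0.41 to 0.40 at 1 month and 0.28 at 3 months. These are uncontrolled changes, but they suggest that vision is still improving after week 4. Section 4.5 also lets treatment stop on resolution and restart on recurrence.

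**Working it through.** **Inputs (section 4.7):** difference 5 letters, SD 9, baseline correlation 0.5, follow-up correlation 0.8, 45 per group, two-sided 5%. Visits are from section 4.6.1. The effect profiles over time are assumptions, because the protocol gives none.

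**Step 1: reproduce the plan's figure.** For the mean of r follow-ups adjusted for baseline, the variance factor is (1 + (r − 1) × 0.8)/r − 0.5².
- r = 2: 1.8/2 − 0.25 = 0.65; SD = 9 × √0.65 = 7.256; n = 2 × (1.960 + 1.282)² × 7.256²/5² = 44.26, rounded up to 45. The stated figure is reproduced.
- r = 1 (12-month contrast, complete data): 1 − 0.25 = 0.75; SD = 7.794; n = 51.07, rounded up to 52.
- r = 5 (average over all visits): 4.2/5 − 0.25 = 0.59; SD = 6.913.

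So 45 per group fits an average of two follow-ups, not a 12-month contrast.

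**Step 2: power and precision of a fixed 12-month contrast.**
- At 45 per group, SE = 7.794 × √(2/45) = 1.643 and 5/1.643 − 1.960 = 1.083, giving 86.1% power.
- 104 less 15% is 88, or 44 per group, giving 85.3%.
- With 52 observed per group, power is 90.5%.
- SE relative to the five-visit average: √(0.75/0.59) = 1.13, about 13% larger.

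**Step 3: simulate the rule.** Thousands of trials were simulated per profile, with 45 per arm and complete data. Baseline-adjusted treatment effects were estimated at five visits, and a 4-df interaction test was applied at 5%. If significant, the 12-month contrast was used; otherwise the equal-weight average. Each profile lists the true effect in letters at week 4 and months 3, 6, 9 and 12.

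| Profile | Rule rejects | Fixed 12-month contrast rejects | Other results for the rule |
|---|---|---|---|
| 5, 5, 5, 5, 5 | 92% | 85% | mean 4.99; coverage about 95% |
| 0, 0, 0, 0, 0 | about 5% | about 5% | no inflation |
| 3.5, 4.5, 5, 5, 5 | 87% | 85% | mean 4.7; coverage 94% |
| 2, 3, 4, 4.5, 5 | 81% | 85% | interaction found in 58%; mean 4.6; coverage 91% |
| 1, 2, 3, 4, 5 | 81% | 85% | interaction found in 84%; mean 4.8; coverage 92% |
| 3, 3, 2, 1, 0 | 10% | about 5% | true pooled effect 9/5 = 1.8 |
| 3, 2.5, 2, 1, 0 | 12% | 5% | interaction missed in 43%; coverage 88% |
| 5, 3.75, 2.5, 1.25, 0 | 6% | 5% | interaction found in 97% |

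**Step 4: sensitivity outside the protocol.** If follow-up correlation decays as 0.9^(months apart/3), profile 3, 3, 2, 1, 0 gives 15-16% rejection. Profile 2, 3, 4, 4.5, 5 gives a mean of 4.4, power of 76-77% and coverage of 89%, with the interaction found in 36%.

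**The case against.** The strongest defence is that the rule often works well. Section 4.7 states one 5-letter difference and no time profile. If the effect is constant, the pooled estimate is unbiased and gains about 7 points of power. With an early plateau the rule still has slightly more power than the fixed contrast. Large trends are nearly always detected. All of this stands, and it limits the harm to moderate trends.

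Three stronger readings are tempting, and the protocol does not support them.

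- A reader might infer that no 12-month effect is estimated unless the interaction is significant. Section 6.1 is silent on that branch, and its closing words on the 12-month effect could be read as unconditional. Even so, the only treatment estimate in a model without the interaction is the pooled coefficient. The label may say 12 months, but it then rests on constancy.
- A reader might infer that the rule inflates type I error generally. It does not: with no effect at any visit the error is close to 5%. The 10% figure needs a real early benefit that has gone by month 12.
- A reader might infer that recurrence, and so a fading effect, is expected. Section 2.1 says there are no data on recurrence after stopping and reports benefit maintained 5 months after stopping in two patients. Section 2.3 describes one recurrence. Section 4.5 restarts treatment on recurrence, which works against complete loss. Slow build-up is the better supported pattern, and there the rule errs towards understating benefit.

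The SAP, not seen here, may settle the matter. The conditional rule is nevertheless written in the protocol, so it is not simply a detail left for later.

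**Conclusion.** The point holds. Sections 4.2 and 4.6.1 fix the primary question at 12 months, while section 6.1 lets an interaction test decide whether that quantity or a pooled one is reported. Section 4.7 matches neither exactly, since it is sized for the mean of two follow-ups.

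The size depends on the effect profile. There is no bias under a constant effect. In the moderate build-up examined, the loss is about 0.4 letters, 4 points of power and 4 points of coverage. In the moderate fading profiles, rejection is 10-12% where 5% is intended. The figures assume complete data, the section 4.7 correlations and an equal-weight average. The larger distortions in Step 4 rest on a correlation pattern that the protocol does not state.

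It should be corrected because it governs the trial's single primary conclusion.

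**What to change.** In section 6.1, and in the SAP to match, delete the significance condition. Always fit treatment, visit, treatment-by-visit and baseline BCVA. Name the treatment difference at the 12-month visit from that model as the single primary result, and report the average over visits as supportive. Use the same approach for secondary outcomes analysed by repeated measures.

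The wording change is small, but it has a statistical cost that should be stated openly. The SE is about 13% larger than for the five-visit average. The stated 90% power should be restated as about 85-86% for the 12-month contrast at 44-45 observed per group. Keeping 90% needs 52 observed per group: 104/0.85 = 122.4, so about 123-124 randomised with 15% dropout.

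If the sponsor prefers the average over visits, which is closer to the basis of section 4.7, it should instead redefine the primary outcome and the hypothesis in sections 4.2 and 4.6.1 in those terms. Either choice must be fixed before unmasking.

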## **6.2 Subgroup analyses**

No subgroup analyses are currently planned. However, depending on the level of adherence observed during the trial, and the ability of participating centres to carry out OCT angiography, two subgroup analyses may be carried out, testing the following interactions:

1. Interaction of good/poor adherence (to be defined) and treatment;
2. Interaction of the presence/absence of new vessels (determined by OCT angiography) and treatment.

If accruing data indicate that these subgroup analyses could be informative, further details will be included in the statistical analysis plan.

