#### 4.4.2 Exclusion criteria

Participant may not enter study if ANY of the following apply

1. Hyperkalaemia (serum potassium level > 5.0 mmol/L).
2. Hepatic or renal impairment (Patients with severe renal insufficiency (Estimated glomerular filtration rate, eGFR < 30 mL per minute per 1.73 m^2) or Patients with severe hepatic insufficiency (Child-Pugh Class C).
3. Pregnancy or breast feeding.
4. Known allergy to fluorescein or indocyanine green.
5. Patients receiving potassium-sparing diuretics, potassium-supplements, or inhibitors of CYP 3A4 (e.g. amiodarone, diltiazem, fluconazole, itraconazole, ketoconazole, ritonavir, nelfinavir, saquinavir, clarithromycin, telithromycin, erythromycin, verapamil, spironolactone and nefazodone)). Patients taking furosemide are eligible.
6. Patients receiving nonsteroidal anti-inflammatory drugs (NSAIDs) (e.g. ibuprofen, naproxen).
7. Patients receiving the combination of an angiotensin converting enzyme (ACE) inhibitor and an angiotensin receptor blocker (ARB).
8. Patients receiving lithium, cyclosporine or tacrolimus.
9. Hypersensitivity or known allergy to eplerenone or to any of the excipients.
10. Known hereditary problems of galactose intolerance, the Lapp lactase deficiency or glucose-galactose malabsorption.
11. Patients receiving high doses of aspirin (>75mg).

The following additional exclusions apply to a study eye only (i.e. they may be present for a non-study eye):

12. Evidence of choroidal neovascularization.
13. Previous or current treatment with eplerenone for any reason or previous or current treatment with photodynamic laser therapy / any anti-VEGF therapy in the study eye / any intra-ocular steroid use / thermal laser therapy for CSCR.
14. Presence of any other disease which could cause retinal fluid or SRF to accumulate (e.g. diabetic retinopathy\*, polypoidal choroidal vasculopathy, domed shaped maculopathy or choroidal haemangioma) or affect visual acuity.
15. Myopia > -6 dioptries

\*Diabetes alone is not an exclusion criterion.

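### The optional treatment-by-adherence interaction in sections 6.1 and 6.2 stratifies on a post-randomisation variable and can show an effect modification that does not exist; the image defining the new-vessel subgroup should also be fixed as pre-dose

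*Protocol*

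**What the plan says.** Section 6.2 opens with "No subgroup analyses are currently planned". It then says that two interaction analyses may be done, depending on the adherence observed and on centres' ability to perform OCT angiography:

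- "Interaction of good/poor adherence (to be defined) and treatment"
- "Interaction of the presence/absence of new vessels (determined by OCT angiography) and treatment"

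Detail is deferred to the SAP: "If accruing data indicate that these subgroup analyses could be informative". Section 6.1 separately allows an analysis of the interaction between adherence and treatment, again depending on the adherence seen. Section 4.5 measures compliance by capsule count at each visit, as pills taken relative to pills prescribed; 70% or less counts as non-compliant for that period.

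Section 6.2 does not say which OCT angiography image defines new-vessel status. A note to Table 1 reads "OCT angiography will be collected at baseline, or at an interim time-point if imaging equipment is not available at baseline, and at 12 months", and section 5.3 likewise allows the first image at "or an interim follow-up visit if equipment becomes available a later date, and at the 12 month follow up". In a study eye, "Evidence of choroidal neovascularization" is an exclusion (section 4.4.2), while section 8.1 lists incident choroidal neovascularisation among the expected adverse events.

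**The concern.** A treatment-by-subgroup interaction compares the treatment effect between strata. Randomisation protects each within-stratum comparison only if stratum membership could not have been influenced by treatment. Adherence fails that condition whatever cut-off is chosen, so leaving the definition to the SAP cannot repair it. A poor adherer on eplerenone may be someone with side effects; a poor adherer on placebo may be someone whose vision is not improving. Comparing the two is not a randomised comparison.

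The protocol makes different links in the two arms plausible. Section 8.1 cites hyperkalaemia in 8.7% on eplerenone and 4% on placebo in a heart-failure trial, and section 4.5 ties treatment cessation both to complications and to resolution of subfoveal fluid.

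What is at stake is a secondary claim. Because the interaction is named in advance, a spurious result could be reported as a prespecified finding about who benefits.

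**Working it through.** **Inputs.** From section 4.7: difference 5 letters, SD 9, baseline to follow-up correlation 0.5, two follow-up assessments correlated 0.8, 90% power, two-sided 5%. Assumed, because the protocol gives no figures: 25% poor adherers in each arm, and correlations r between a latent adherence variable and outcome.

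**1. The plan's own figure.** Variance factor = (1 + 0.8)/2 − 0.5² = 0.65. Effective SD = 9 × √0.65 = 7.256 letters. Patients per group = 2 × (7.256 × (1.960 + 1.282)/5)² = 44.3, so 45, with power 90.5%. The stated 45 reproduces, and 7.256 is the SD used below.

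**2. Expected spurious interaction when the drug has no effect.** The lowest 25% of a standard normal variable has mean −1.271 and the remaining 75% has mean +0.424, a gap of 1.695. In an arm with correlation r, good and poor adherers therefore differ by r × 1.695 × 7.256 = 12.30 × r letters. The interaction is the difference of this quantity between arms: 12.30 × (r placebo − r active). For 0.3 and 0 it is 3.7 letters; for equal correlations it is zero.

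**3. Precision.** With 45 per arm and 25% poor adherers, the standard error of the interaction is 7.256 × √[2 × (1/11.25 + 1/33.75)] = 3.53 letters. A real 5-letter interaction would have only about 29% power.

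**4. Simulation of the interaction test.** No drug effect in any patient, two-sided 5%, 8,000 trials per row.

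| r placebo / r active | Mean interaction, N=90 (letters) | False positives, N=90 | False positives, N=104 |
|---|---|---|---|
| 0 / 0 | 0.0 | 5.0% | 5.1% |
| 0.3 / 0.3 | −0.1 | 5.0% | 4.7% |
| 0.3 / 0 | 3.7 | 16.9% | 19.9% |
| 0.5 / 0.2 | 3.7 | 17.6% | 20.1% |
| 0.5 / 0 | 6.2 | 42.0% | 46.4% |
| 0.3 / −0.3 | 7.5 | 55.2% | 62.2% |

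The means agree with step 2. The error comes from the difference in correlation between arms, not from its level.

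**5. Direction.** With r = 0.3 on placebo only, placebo means are −0.3 × 1.271 × 7.256 = −2.8 letters (poor adherers) and +0.3 × 0.424 × 7.256 = +0.9 (good adherers); eplerenone means are 0 in both. The drug then appears 2.8 letters better in poor adherers and 0.9 worse in good adherers. With the link on eplerenone only, the signs reverse.

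**6. New-vessel factor.** Assumed, with N=90: 20% of patients have new vessels at baseline, unrelated to outcome; among patients imaged at an interim visit, 15% of those on placebo, and none on eplerenone, have incident vessels (correlation 0.5 with outcome).

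| Share of images that are interim | Mean interaction (letters) | False positives |
|---|---|---|
| 0 | −0.1 | 5.0% |
| 25% | 0.9 | 6.2% |
| 50% | 1.8 | 8.1% |
| 100% | 3.1 | 14.2% |

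**The case against.** **The analyses are optional and unfinished.** Section 6.2 says so, and the SAP could define the adherence cut-off and choose the image. This stands for the image. It does not stand for adherence, where the fault lies in the variable and not in its cut-off.

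**A bias needs different links in the two arms.** This stands: with equal correlations the test holds its level. Since pills are counted against pills prescribed, stops directed by the protocol need not register as poor adherence, which narrows the side-effect route. Stopping on the patient's own initiative remains.

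**Stronger readings that the protocol does not support:**

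- A reader might infer that a null drug would come out as working in adherent patients. The direction depends on the assumed links; a placebo-only link gives the false benefit to poor adherers.
- A reader might infer that the new-vessel subgroup is equally faulty. Baseline OCT angiography is the default and a valid factor; the interim image is a fallback, "at an interim time-point if imaging equipment is not available at baseline". The problem arises only if interim or 12-month images define the subgroup, and even under strong assumptions it is smaller.
- A reader might infer from the reference to accruing data that the tests would be chosen on the results. The triggers named are the level of adherence and equipment, and section 6.1 has the SAP written before any comparative analysis.

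**Conclusion.** The point holds for adherence and, conditionally, for the new-vessel factor. The treatment-by-adherence interaction rests on a variable measured after randomisation in every patient, and no definition in the SAP can change that. Under the central assumption (25% poor adherers, correlations 0.3 on placebo and 0 on eplerenone, 90 patients) the false-positive rate is about 17% and the spurious interaction 3.7 letters, roughly one standard error. Across the assumptions tried with N=90 the rate runs from 5% (equal links) to 55% (opposite links). The correlations, the share of poor adherers and the vessel rates are all assumptions, so these figures show what can happen and do not predict what will.

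The new-vessel subgroup needs one clarification, the image to be used. Nothing here affects the primary intention-to-treat analysis or the sample size. The change is worth making, but the trial's main conclusion does not depend on it.

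**What to change.** 1. Remove the adherence-by-treatment interaction from sections 6.1 and 6.2. Adherence can still be described by arm.
2. If an adherence question is kept, estimate a complier-average causal effect in all randomised patients, with allocation as the instrument, and label it exploratory. State the complier definition and the exclusion restriction: allocation has no effect on outcome in non-compliers. That assumption is open to doubt here, since a patient below a pill-count cut-off has still taken some drug. With no drug effect the estimate is centred on zero, as the intention-to-treat difference is.
3. State in section 6.2 that new-vessel status is taken from OCT angiography performed before the first dose. Patients with only later images stay out of that subgroup but remain in every other analysis. With baseline images only, the simulated error rate is 5.0%.

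The cost is a few sentences, one extra model if item 2 is used, and fewer patients in the OCT angiography subgroup. Because study eyes with evidence of neovascularisation are excluded at entry, the group with vessels present may be small; its size should be checked before the test is committed to.
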